- To compare the effect of RAGT by use of the Atalante self-balance exoskeleton with conventional Rehabilitation training (cRHB), for improving **static balance**, **dynamic balance**, mobility, and **self-perception of gait impairment** measured with:
 - **Static Balance** by the Berg Balance Scale (BBS), considering a clinically relevant change for improvement in balance as measured by BBS was +3 points, meaning that PwMS are likely to perceive that as a reproducible and clinically important change in them balance performance.¹⁷
 - **Dynamic balance** by the Timed Up and Go test (TUG)¹⁸
 - **Mobility** measured by modified Rivermead Mobility Index (mRMI)¹⁹

- **Self-perception of gait** impairment by Multiple Sclerosis Walking Scale-12 (MSWS-12)²⁰
- **Instrumented gait analysis** by the G-walk device (assessing gait cycle duration, step length, propulsion index, support phase percentage D/I, oscillation phase percentage D/I, double/unique support phase percentage).
- To compare the effect of RAGT by use of the Atalante self-balance exoskeleton with conventional Rehabilitation training (cRHB) on quality of life, emotional status and fatigue measured at pre and post-intervention with:
 - Multiple Sclerosis Quality of Life-54 (MSQoL 54 Health Survey Spanish version)²¹
 - Hospital Anxiety and Depression Scale (HADs) considering a clinically relevant change of 1.7 points at HADs²²
 - The Modified fatigue scale (MFIS) ^{23 24}
 - The patient' physical effort of each session by means of the scale of perception of the effort R.P.E of Borg at the end of each training^{25 26}.
 - To evaluate the epigenetic blueprint of rehabilitation training by comparing the genome wide chromatin accessibility of peripheral blood mononuclear cells (PBMCs) before and after RAGT or cRHB, by Assay for Transposase-Accessible Chromatin sequencing (ATACseq).
 - To test the hypothesis that genome wide chromatin accessibility compared to clinical measures can be useful for identifying molecular mechanisms underlying rehabilitation therapies.
 - To compare the changes induced by RAGT versus cRHB on the overall chromatin accessibility, and specific genome regions and pathways.
 - Use the biological samples to provide additional functional and mechanistic information about the rehabilitation effects and subject health, disease or state.

3 Materials And methods

3.1 Design:

This trial is a prospective, randomized, rater-blinded study (cRHB (N=30) vs RAGT (N=30)).

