For the control group, this protocol includes 24 one-hour sessions of cRHB training during 8 weeks three times per week, under the supervision of a qualified rehab team.

For the intervention group (RAGT) this protocol includes 24 one-hour sessions of RAGT during 8 weeks three times per week, under the supervision of a qualified rehab team.

Additionally, peripheral blood (6ml) will be taken from all subjects at three timepoints: at baseline (T1), after the 8 weeks of rehabilitation treatment (T2) and, if possible, one year after T4. Biological samples will then be given a unique identifier and transferred to researchers for analysis.

Informed consent will be obtained from patients prior to inclusion in the study, which will be carried out in accordance with the Declaration of Helsinki.

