3.4 Assessments

The following information will be collected for all patients: age, sex, weight, height, type of MS, years from the diagnosis, Expanded Disability Status Scale (EDSS) and type of support device.

To ensure that training sessions are well tolerated, we will assess patients' blood pressure and heart rate weekly. We will also monitor the appearance of pain in any part of the body related to the RAGT at end of each training session using a pain registry (type of pain, location, intensity)²⁷.

3.4.1.1 To reduce the incidence of any type of muscle injury the physical therapist before each RAGT session will assess the level of spasticity using the Numeric Rating Scale measure of spasticity (NRS). The 0–10 NRS asks patients to indicate their level of spasticity on a scale of 0–10, where 0 is no spasticity and 10 is the worst possible spasticity. This type of rating tool is widely utilized in clinical settings to quickly assess pain.²⁸

A record of any unexpected Serious Adverse Events (SAE) within trial episodes will be kept. These are defined as death, a life-threatening adverse event or an event occurring as a result of the use of the device that requires medical intervention.

After the 8 weeks of rehabilitation treatment (T2) and, if possible, one year after T4, peripheral blood (6ml) will be taken from all subjects to perform the subsequent molecular analysis.

Molecular analysis

Peripheral blood mononuclear cells (PBMCs) will be purified using the Ficoll-Hypaque density gradient method according to manufacturer's instructions. Briefly, whole blood will be extracted by venepuncture and collected in CPT Vacutainer tubes (Becton Dickinson, BDAM362781) and centrifuged at 2250g for 25 min. Supernatant will then be collected, and washed twice with enriched saline (0.9% NaCl, 2%FBS). PMBC containing pellet will then be resuspended with 1 ml of complete media (RPMI1640 + 2% FBS) and cells will be counted and assessed for viability using a Countess 3 automated cell counter (Invitrogen). PBMCs will be adjusted to 5×10^6 cells/ml in freezing media media (90% FBS, 10% DMSO), and frozen at -80°C using a [name]™ Freezing Container (Thermo Scientific™) for 24 h and stored in liquid nitrogen vapor phase.

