	Running treadmill with speed and inclination according to tolerance (2-6 minutes)	Passive verticalization at standing or inclined plain to reduce the flexor musculature hypertonia (10 minutes)	If MB = 5: active-resisted exercises with 2 kg of major glutes, psoas, quadriceps, hamstrings and anterior tibial (3 sets of 5 repetitions for each muscular group)
	Weight-bearing walking (5 minutes).	Active verticalization at the shoulders or parallel bars in order to reduce the hypertonia of the flexor muscle (5-10 minutes)	Step from sitting to standing (3 sets of 5 repetitions)
	Vibratory stimulation in bilateral plantar zone (5 minutes)	Antero-posterior and lateral pelvic tilting exercises to encourage straightening reactions and reduce upper limbs hypertonia. (5-10 minutes)	Go up and down 20 stair's steps
		Pelvic and trunk rotations to decrease trunk extension hypertonia (5 minutes)	Active-resisted cycloergotherapy, resistance according to symmetry (10 minutes)
		Passive cycle ergotherapy adapting speed to tolerance and avoiding spasms during exercises (10 minutes).	

Atalante Gait training (RAGT):

Participants randomize to receive a Atalante gait training, will be trained 3-times per week, with an intensity of 40 to 60 minutes, and duration over 8-weeks. Progression will occur by increasing the session intensity weekly. Training intensity will be monitored and standardized using the Borg Rating of Perceived Exertion scale, and will progress from 'fairly light' to 'somewhat hard'. This prescription is consistent and appropriate for individuals with MS with mobility impairment and low fitness levels. Progression will occur by increasing the intensity of the session increase the number of steps in each session and decrease the level of assistance. Sessions will not exceed 60 minutes. We will record all training parameters.

Using the Atalante System, participants will be secured with the appropriately sized harness and attached to an overhead body-weight support system. Each session will begin with a 3–5-minute warm-up in the continuous passive mode (cadence ~40-45 steps/minute). The participant will then be transitioned into the adaptive training phase for practicing repetitive floor walking for up to 30 minutes. During this phase, the force produced by the robot is modulated to support the effort of the patient in producing a typical walking pattern.

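### Events needing medical intervention count as SAEs only if the device caused them, so below the life-threatening level they can be recorded only in the RAGT arm

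*Combined protocol and SAP*

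**What the plan says.** Section 3.1 sets out two arms of equal size: "This trial is a prospective, randomized, rater-blinded study (cRHB (N=30) vs RAGT (N=30". The control arm gets conventional training only: "For the control group, this protocol includes 24 one-hour sessions of cRHB training during 8 weeks three times per week". Neither Section 3.1 nor the control programme in Section 3.6 gives control patients any time in the exoskeleton.

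The rule for serious harms is in Section 3.4. On what is kept, it says: "A record of any unexpected Serious Adverse Events (SAE) within trial episodes will be kept". On what qualifies, it begins "These are defined as death, a life-threatening adverse event or an event" and completes the third category as "an event occurring as a result of the use of the device that requires medical intervention".

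The same section describes other tolerability checks. Vital signs are worded for patients in general: "we will assess patients' blood pressure and heart rate weekly". Pain at the end of sessions is tied to one arm; staff will "monitor the appearance of pain in any part of the body related to the RAGT at end of each training session". The spasticity rating before sessions is likewise described for RAGT sessions. In Table 1 the session-level column is headed for the robotic sessions, although pain, vital signs and spasticity are also scheduled at assessment visits.

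**The concern.** A seriousness criterion should turn on what happened to the patient. Here the third category turns on what caused the event, and the named cause exists in one arm only. A control patient cannot meet it, however bad the injury, unless the event is fatal or life-threatening.

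This matters because the control programme carries physical risk of its own. Section 3.6 lists, among other items, "Running treadmill with speed and inclination according to tolerance (2-6 minutes", stair climbing, trunk work on an unstable surface and standing balance work, in patients with EDSS 6.0 to 7.0 (Section 3.2.1). A fall injury there that needed medical care would leave no trace in the SAE record. A reader of the results could then take a control count of zero in this category as evidence about conventional training, when it follows from the definition alone.

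A second and separate matter is that only *unexpected* events are kept. The plan does not say what is expected. On the ordinary meaning of the word, a serious event that staff could foresee may be left out in either arm.

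**Working it through.** The plan states no event rate, count or power for harms, so there is no figure of its own to reproduce. The check is first a reading of the rule by category and by arm, and then an illustration with assumed rates.

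**Step 1: the rule by arm (Section 3.4, with Sections 3.1 and 3.6 for exposure).**

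| Category | Condition on the device | Recordable in RAGT | Recordable in control |
|---|---|---|---|
| Death | none | yes, if unexpected | yes, if unexpected |
| Life-threatening event | none | yes, if unexpected | yes, if unexpected |
| Event requiring medical intervention | must result from device use | yes, if unexpected and attributed to the device | no |

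The asymmetry sits in the third row and comes from the device condition alone. The *unexpected* limit applies to every row and both columns.

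**Step 2: does anything else in the plan catch a control injury?** Vital signs do not record injuries. Pain and spasticity ratings at scheduled visits give a level at that visit, not an event with its treatment. The session-level checks are worded for RAGT. Section 3.4.2 counts a cancelled session as missed and asks for no reason. No collection of adverse events that applies equally to both arms appears in the documents.

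**Step 3: size, for illustration only.** Inputs: n = 30 per arm (Section 3.1). Assumptions, not in the documents: the same true proportion p of patients with a third-category type of event in each arm, and every RAGT event attributed to the device and recorded.

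- Expected RAGT records = 30 × p. Recorded control events = 0, by definition.
- p = 5%: 30 × 0.05 = 1.5 against 0.
- p = 10%: 30 × 0.10 = 3 against 0.
- p = 20%: 30 × 0.20 = 6 against 0.

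Under equal rates, the same 1.5, 3 or 6 events would be expected in control and lost.

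If only a fraction a of RAGT events is attributed to the device and recorded, the expected count is 30 × p × a. With a = 0.5 and p = 10%, that is 30 × 0.10 × 0.5 = 1.5, still against 0. The figures with a = 1 are thus the largest gap at each rate.

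**Step 4: could the artefact look like a finding?** For x of 30 against 0 of 30, the two-sided Fisher p-value is 2 × C(30,x)/C(60,x). It is 0.052 at x = 5 and 0.024 at x = 6, so six events is the first count below 0.05. With X distributed as Binomial(30, p), the chance of X ≥ 6 is 0.3% at p = 5%, 7.3% at 10% and 57% at 20%. A nominally significant artefact is therefore unlikely unless such events are common. The plan does not propose this test.

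**The case against.** The best case for the plan is that the gap is narrow and that no planned analysis depends on it. Several parts of that case stand.

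- A reader might infer that harms are captured in one arm only, or that the control SAE count must be zero. Section 3.4 does not support this: deaths and life-threatening events are recordable in both arms and can be compared, and vital signs and the visit ratings of pain and spasticity are not confined to RAGT.
- A reader might blame the word *unexpected* for the imbalance. By its wording it narrows both arms alike.
- A reader might infer that falls are certain to be excluded as expected, because the introduction mentions a high risk of falls. That text lists it among factors that limit some patients' participation in therapy. It does not classify fall injuries as expected events, so their exclusion is possible but not established.
- A reader might infer that unblinded treating staff decide whether the device caused an event. The documents do not say who decides.
- Safety is not among the aims in Section 2. Section 4 gives a general method for comparing proportions but names no harm outcome, and the primary outcome, the 10-metre walk test, is untouched.
- The rates in the illustration are assumed, and the attribution and *unexpected* conditions would reduce the RAGT count as well.

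None of this removes the third-category gap. Any report of harms by arm, planned or not, would inherit it, and events not recorded during the trial are hard to recover reliably afterwards. The objection also shows that striking out the device clause and nothing else would be a poor repair, since any event needing any medical care would then become serious.

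**Conclusion.** The point holds in a limited form. Non-life-threatening events that need medical intervention can be recorded as SAEs only in the RAGT arm. Together with session-level pain and spasticity checks worded for RAGT, this means that such harms cannot be compared between arms. This is the effect of a stated rule followed exactly, not of a missing detail.

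The conclusion that no safety statement at all is possible would go too far, because fatal and life-threatening events remain comparable, subject to the *unexpected* limit.

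The structural zero in control rests on the text alone. The size in RAGT (1.5, 3 or 6 of 30) rests on assumed equal rates of 5%, 10% or 20% and on full attribution and recording. The possible loss of foreseeable serious events is a second defect, common to both arms; its size cannot be judged because the term is undefined. The matter should be corrected, but it does not threaten the primary comparison.

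**What to change.** Rewrite the SAE paragraph in Section 3.4 as follows.

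1. Remove *unexpected* and the device condition as conditions for entering the record.
2. Apply one outcome-based definition of a serious event to both arms. Word the medical-intervention criterion so that routine minor care does not qualify.
3. Replace the limit to trial episodes with a stated recording period that is the same in both arms, with its end tied to a named visit. Table 1 runs clinical tests to T3 and blood sampling to T4, so the closing visit has to be named.
4. Record expectedness, and relatedness to the device or to the study training, as separate fields for every event.
5. Report counts descriptively by randomised arm.

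Unless the session-level pain and spasticity checks are also recorded in control, the report should present them as RAGT-only data.

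The cost is one protocol paragraph and one adverse-event form used in both arms, with some care over the wording in items 2 and 3. The small downside is more events to record. The change affects recording and reporting only.

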Once all samples are collected, chromatin will be extracted from the frozen PBMCs. Briefly, each vial containing 5×10^6 cells will be thawed and centrifuged at 300g for 5 min at 4°C . The supernatant will then be removed, and cells will be mixed with 100 μL of lysis buffer (10 mM NaCl, 3 mM MgCl₂, 10 mM Tris-HCl pH7.4, 0.1% Tween-20, 0.1% NP40) and lysed on ice for 4 min. Followed by 2x1ml washes (10 mM NaCl, 3 mM MgCl₂, 10 mM Tris-HCl pH7.4, 0.1% Tween20) before centrifuging at 500g for 5 min at 4°C .

Next, ATAC-seq libraries will be generated according to manufacturer guidelines. Briefly, transposition mix (Illumina, Cat# 20031198) will be added to the nuclear pellets, incubated at 37°C for 30 min, and DNA purified using the QIAGEN MinElute PCR Purification Kit (QIAGEN, Cat#28004). DNA fragments will be amplified by PCR for 10 to 11 cycles and resulting libraries purified using the QIAGEN MinElute PCR Purification Kit. The libraries will then be sequenced with an Illumina Novaseq 6000 S4 flow cell using 150 bp paired-end reads (Illumina, Cat# 20027466). FASTQ files will be generated from the NovaSeq BCL outputs and used as input to the ENCODE ATAC-seq pipeline (<https://github.com/ENCODE-DCC/atac-seq-pipeline>) using the MACS2 peak-caller with all default parameters. Differential accessibility will be initially calculated between groups using the csaw package.

To identify differentially open chromatin regions between groups from ATAC-seq, the R package edgeR will be used to fit a generalized linear model (GLM) to test for the effect of rehabilitation between T0 and T1 samples. In addition to time group (T0 vs. T1), we will also compare the two different rehabilitation treatments (cRHB vs. RAGT at T1). We will also use surrogate variable analysis (SVA) to capture unknown sources of variation (e.g., batch effects, age, sex, library preparation, etc) statistically independent from time or treatment group assignments. SVA decomposes the variation that is not accounted for by known factors such as time group or treatment into orthogonal vectors that can then be used as additional covariates when fitting a model to test for differential accessibility or expression.

Benjamini-Hochberg P value correction will be used to select differentially open peaks at an FDR of 5%.

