Differentially open ATAC-seq peaks will then be annotated with regard to functional and positional information. HOMER will be used to annotate peaks based on the relative gene position (promoter (± 2 kb of known TSS), intergenic,

intronic, among others). For functional annotation of peaks, we will use a simplified version of the 18-state ChromHMM-derived chromatin states (such as TSSs, enhancers, repressed polycomb, transcriptionally active, or other states such as ZNFs or heterochromatin) obtained from Roadmap Epigenomics data for PBMC and T cell subsets.

For gene-based analyses, HOMER will be used to assign each differentially open ATAC-seq peak to the nearest TSS, as measured from the peak center. We will then assess enrichment using the hypergeometric test followed by Benjamini-Hochberg FDR adjustment for P values, as previously mentioned.

Further functional and ontological enrichment analyses will be performed using ClueGO and WikiPathways that will allow us to identify pathways among genes associated to differentially open peaks.

Finally, we will scan the data for transcription factor (TF) footprints using the PIQ algorithm which integrates genome-wide TF motifs with chromatin accessibility estimates profiled at base pair resolution to generate a list of possible footprint matches for a motif. In a nutshell, this will allow the identification of chromatin accessibility blueprint generated by the different rehabilitation therapies tested in this trial, as well as gather valuable data of its underlying molecular mechanisms that in turn might lead to the identification of novel therapeutic targets.

Type outcome	Test	Baseline (T1)			RAG Session 1-24 (S1-S24)			end of training (T2)			Follow up at 2 months (T3)			Follow up at 1 year (T4)		
		CRO	PROMs	Blood sample	CRO	PROMs	Blood sample	CRO	PROMs	Blood sample	CRO	PROMs	Blood sample	CRO	PROMs	Blood sample
Pain	1	Pain registry		x			x			x			x			
Physiologic indicators	2	Heart rate	x			x			x			x				
	3	Arterial pressure	x			x			x			x				
Effort	4	Rating perception exertion The Borg R.P.E scale				x										
Fatigue:	5	Modified fatigue scale (MFIS)		x						x						
Depression	6	Hospital Anxiety and Depression Scale (HADS)		x						x						
Health-related quality of life	7	MSQoL 54 Health Survey		x						x						
Mobility	8	Modified Rivermead Mobility Index	x						x			x				
Disability	9	Expanded Disability Status Scale (EDSS) de Kurtzke	x						x			x				

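### The before-after ATAC-seq contrast is labelled the effect of rehabilitation, but with both arms training and no untreated group it estimates uncontrolled change over 8 weeks

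*Combined protocol and SAP*

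**What the plan says.** Section 2.2 sets out to find the epigenetic blueprint of rehabilitation by "comparing the genome wide chromatin accessibility of peripheral blood mononuclear cells (PBMCs) before and after RAGT or cRHB". A further aim in the same section is to compare how much the two therapies change accessibility.

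Section 3.4 (Molecular analysis) turns these into two contrasts. The first is a "generalized linear model (GLM) to test for the effect of rehabilitation between T0 and T1 samples". The second follows: "In addition to time group (T0 vs. T1), we will also compare the two different rehabilitation treatments (cRHB vs. RAGT at T1". No arm-by-time term is written. Surrogate variable analysis (SVA) is added for unknown variation, described as statistically independent of time and treatment. Peaks are selected by Benjamini-Hochberg (BH) at a 5% false discovery rate (FDR). They then pass to annotation, pathway and footprint steps, summarised as the "identification of chromatin accessibility blueprint generated by the different rehabilitation therapies tested in this trial".

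Section 3.1 gives two arms of 30. For the control arm, "this protocol includes 24 one-hour sessions of cRHB training during 8 weeks three times per week"; for the other, "this protocol includes 24 one-hour sessions of RAGT during 8 weeks three times per week". There is no untreated or waiting-list group.

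On processing, Section 3.4 states: "Once all samples are collected, chromatin will be extracted from the frozen PBMCs".

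**The concern.** A comparison of two dates in people who all trained shows whether accessibility changed between those dates. It does not show that training caused the change. Yet the plan words the contrast as a test of rehabilitation and describes its output as produced by the therapies. If the plan is followed as written, peaks, pathways and footprints that reflect other changes over the period could be published as therapy effects.

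One technical difference is aligned with time by design. Cells are frozen at each visit and chromatin is extracted after collection ends, so each patient's baseline vial is stored about 8 weeks longer than that patient's post-training vial.

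The one contrast protected by randomisation is written as a comparison at a single visit, whereas Section 2.2 aims at a comparison of changes.

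**Working it through.** **No plan figure to reproduce.** The only sample-size figure, 15 in Section 4, concerns walking performance. No ATAC-seq power or sample size is stated.

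**What each contrast estimates.** For one peak, let R_a be the effect of training in arm a, δ any other change over the 8 weeks, assumed common to both arms, and e random variation with mean zero. The change in a patient of arm a is D = R_a + δ + e.

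- Mean change, both arms pooled: (R_RAGT + R_cRHB)/2 + δ.
- Mean change, one arm: R_a + δ.
- Difference in mean change between arms: R_RAGT − R_cRHB. Here δ cancels.

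The first two cannot tell R from δ. The plan does not say whether the time contrast is pooled, and the defect is the same either way.

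**SVA.** In a linear model, a covariate orthogonal to time leaves the time coefficient unchanged. In a simulated set of 120 samples with a linear storage effect, the coefficient was −0.291 both without and with such a surrogate variable.

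**BH.** The null hypothesis it protects is no change over time. A drifting peak is a true change, so flagging it is not a false discovery in the sense that BH controls.

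**How many peaks could be involved.** Inputs from the plan: 60 patients (30 per arm) and 5% FDR. Assumptions: 20,000 peaks, the share drifting, the drift in SD of the within-patient change, no rehabilitation effect, and Gaussian paired tests standing in for the edgeR model.

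Per-peak chance of nominal p<0.05, two-sided noncentral t with noncentrality d√n:

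| Drift d | 60 pairs: d√60 | Chance | 30 pairs: d√30 | Chance |
|---|---|---|---|---|
| 0.2 | 1.549 | 33.2% | 1.095 | 18.5% |
| 0.3 | 2.324 | 62.8% | 1.643 | 35.5% |
| 0.5 | 3.873 | 96.8% | 2.739 | 75.4% |

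The plan selects by BH, not by nominal p, so the next table is the relevant one. It gives mean peaks flagged over 10 simulated repeats:

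| Share drifting | Drift d | Before-after, 60 pairs | Before-after, one arm of 30 | Between-arm difference in change |
|---|---|---|---|---|
| 5% (1,000) | 0.2 | 0.8 | 0.5 | 0.0 |
| 5% (1,000) | 0.3 | 40.2 | 0.6 | 0.3 |
| 5% (1,000) | 0.5 | 768.4 | 156.5 | 0.1 |
| 20% (4,000) | 0.2 | 22.0 | 1.1 | 0.0 |
| 20% (4,000) | 0.3 | 805.4 | 15.6 | 0.0 |
| 20% (4,000) | 0.5 | 3,651.7 | 1,516.7 | 0.0 |

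With no drift, each contrast flagged 0.0 to 0.1 peaks on average. At a 20% share, the pooled counts equal about 0.55% (22/4,000), 20.1% (805.4/4,000) and 91.3% (3,651.7/4,000) of the number of drifting peaks.

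**Visit labels.** Sections 3.1 and 3.3 and Table 1 call baseline T1, and the end of training is T2. The molecular analysis uses T0 and T1. I read its T0 as baseline and its T1 as post-training. Under the schedule's labels, the planned arm comparison at T1 would fall before any training.

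**The case against.** The plan has real protections. Section 3.2.1 requires stable disease-modifying therapy for 6 months. Section 3.2.2 excludes relapse, corticosteroids and therapy changes during the study. Cells are kept in liquid nitrogen vapour, and extraction after collection avoids separate processing campaigns for baseline and post-training samples. A randomised comparison of the arms is already planned, and it too is unaffected by drift common to both. The aim is secondary, and parts of it are worded cautiously. All of this stands. It narrows the sources of drift but does not remove change aligned with time, and the randomised comparison answers a different question: whether the therapies differ.

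Some stronger readings are tempting but not supported:

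- *Any drift will be reported as a rehabilitation effect.* Only drift large enough to pass the FDR threshold is flagged. At 0.2 SD, under 1% of drifting peaks would be.
- *Most drifting peaks would be called even at 0.3 SD.* The 62.8% figure uses nominal p-values and 60 pooled pairs. Under BH with 20% drifting, the figure is about 20%.
- *Storage biases the results.* The documents do not show that 8 extra weeks shifts accessibility. The longer storage is within patient; if entry is staggered, one patient's baseline vial need not be older than another's post-training vial.
- *Season shifts everyone alike.* No enrolment window is given, so neither a common seasonal shift nor its averaging out is established.
- *Pathway and footprint work should use only the between-arm list.* That would discard effects common to both therapies, which the blueprint aim seeks to describe.

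**Conclusion.** The concern holds as a matter of labelling and of which contrast carries the causal claim. The before-after contrast, pooled or within arm, estimates rehabilitation plus other change over 8 weeks, and nothing in the described analysis separates them. This conclusion follows from the design and does not depend on any assumed drift.

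The size is unknown. Under the assumptions stated, 60 pairs could flag from about 1 peak (5% drifting, 0.2 SD) to 3,652 (20% drifting, 0.5 SD) with no rehabilitation effect, against about none for the difference in change. That cancellation requires drift to be equal in the two arms. The primary walking-speed comparison is not affected.

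**What to change.** 1. Label the before-after contrast *change over the 8-week training period (uncontrolled)*. Report its annotation, pathway and footprint results under that label, without causal wording.
2. Replace the single-visit arm comparison with the arm-by-time contrast: difference in change from baseline, with each patient's samples paired in the model. This matches the Section 2.2 aim of comparing changes. Base treatment-attributed statements on it.
3. Reconcile the visit labels between the molecular analysis and the schedule.

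A check of baseline accessibility against days in storage is optional and only exploratory, because storage time coincides with calendar date.

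The cost is SAP wording and a respecified model on data already planned. Fewer peaks will be attributable to treatment. Effects common to both therapies can be described but not attributed to rehabilitation, since this design has no untreated reference. Precision is a further consideration. With equal variances and within-patient correlation ρ, the variance of the difference in change is 2(1 − ρ) times that of a post-training-only comparison, so it is smaller only when ρ exceeds 0.5.
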